2.5.2. Vagal Nerve Stimulation (VNS) – state of the art

Over 100.000 patients have been treated with vagal nerve stimulation (VNS) therapy for epilepsy. The surgical procedure to implant the vagal nerve stimulator is well established and appears to be a relatively safe intervention (Garcia-Navarrete et al., 2013; Kahlow and Olivecrona, 2013; Revesz et al., 2016). VNS surgery is associated with an overall surgical complication rate of 8.5% (Selner et al., 2019). “Surgical complications included infection, vocal cord palsy, post-operative hematoma, intra-operative bradycardia during test stimulation, and others, with infection (3.9%)” (Selner et al., 2019). A 6.5% rate of hardware complications were reported, including lead fracture and stimulator malfunction. Lead fracture was the most common complication (5.6%) (Selner et al., 2019). Overall, the implantation is a safe procedure and well established for more than 25 years (Spuck et al., 2010), and VNS is as a relatively safe treatment (Giordano et al., 2017; Panebianco et al., 2016; Selner et al., 2019).

Specifically with respect to vagal nerve stimulation to control blood pressure, selective stimulation of vagal afferent baroreceptor fibers is preferable to stimulating efferent fibers that may lead to side effects such as bradycardia or heart block (Plachta et al., 2014; Timarova and Steno, 2017). Most of the stimulation associated side effects are derived from stimulation of the inherent functions of the vagal nerve (Timarova and Steno, 2017). The feasibility of selective VNS to elicit baroreflex responses has been shown in rats without occurrence of severe adverse events (bradycardia or heart block) (Plachta et al., 2014). Even when angiotensin converting-enzyme inhibitors (a commonly used antihypertensive medicine) were co-administered with VNS, selective VNS reduced blood pressure (Gierthmuehlen et al., 2016). Moreover, cardiac-cycle-synchronized stimulation triggered to the R-wave of the electrocardiogram in rats successfully reduced blood pressure using constant stimulation parameters with hardly any side-effects (Plachta et al., 2016).

The unique cuff electrode design of the baroloop system permits anatomically selective, vagal nerve stimulation to activate the baroreflex and reduce blood pressure. An implantation procedure similar to that used for VNS to treat epilepsy will be used. However, the lead design of the baroloop system is different, and lead placement has been adapted to the unique aspects of the baroloop design. Nevertheless, similar overall surgically related complications may be expected. Any adverse events associated with VNS using the baroloop device will be evaluated during the proposed First in Human (FIH) study. The anatomically selective stimulation used in the neuroloop system may reduce the occurrence of side-effects associated with VNS, since a relatively higher proportion of baroreceptor active fibers may be stimulated, although the baroloop electrode may include cardiac branches of the vagal nerve. Selective stimulation delivered by the unique neuroloop electrode design may avoid or reduce some of the cardiac side effects related to stimulation of efferent cardiac branches of the vagus, since the targets of baroreflex activation are the afferent baroreceptor fibers.

2.5.3. Neuromodulation: selection of stimulation parameters

Electrical neuromodulation has a long history in humans and a broad scope of targets, including the brain, spine, peripheral nerve, retina, cochlea, etc. (e.g.: ECoG, Retinal Implants, ActiGait, VNS, DBS, SCS). The form and shape of the electrodes (contacts) have to be designed appropriately to fit the target area. The baroloop cuff electrode contains multiple

individual electrode contact areas: cathodes with areas of $264.000 \mu\text{m}^2$ and anodes with areas of $2.34*10^6 \mu\text{m}^2$. The combination of electrode geometry and stimulation parameters (frequency, duty cycle and pulse duration) must be adapted to achieve optimal output and activation of the target and minimal damage to the electrode (corrosion) and the surrounding tissue. An electrode can deliver a certain amount of charge/area without corrosion within the so-called water window within which the charge does not corrode the electrode material nor is water subjected to electrolysis (Cogan, 2008). Pulse width and charge balancing are typical countermeasures to avoid both corrosive processes and changing pH values. The amount of charge to be applied via the electrode contacts is limited not only by material parameters as described above. Thresholds also arise from physiological constraints. The “Shannon Criteria” provide a conservative estimate of the limits of charge that may be safely applied in terms of the amount of charge/area/cycle to avoid neural damage (Shannon, 1992). In most cases, the Shannon Criteria are below the water window of the working electrode.

To evaluate the safety of the stimulation presets used by the baroloop system it is necessary to consider the **total energy delivered** and the **potential for tissue damage** of the electrodes used for neural stimulation, rather than the individual values within each preset. The amount of energy absorbed by the tissue is dependent on many variables, including the stimulus intensity (typically measured in microamperes), the duty cycle, the frequency of stimulation, and the duration of stimulation. Different combinations of these parameters can result in the delivery of the same equivalent energy to the tissue. To provide a common scale to assess ranges of stimulation characteristics, scientists focus on the **number of electrons delivered**. This value is the total electrical charge which is measured in coulombs. One coulomb is equivalent to one ampere x one second ($1 \text{ C} = 1 \text{ A} \times 1 \text{ s}$).

In addition to the number of electrons delivered to tissue, the potential for tissue damage also varies as a function of the **area over which the electrons are delivered** (smaller electrode area for any given charge increases the risk of tissue damage), and so the size of the electrode is a consideration. To account for this, the charge delivered is divided by the geometric surface area of the electrode and expressed as the charge density.

The **charge delivered per phase** also affects the risk of tissue damage. These terms are captured by the Shannon equation and the Shannon limit.

[figure not shown]
The presets defined for use in the baroloop Study are all well below the Shannon limit and within the range tested in animals. In this way, the electrical charge delivered to tissue in all of the FIH preset stimulation sequences is covered by the animal studies. The variety of charges delivered to tissue in the Sponsor's animal studies were all shown to be safe. For more details, please see also Section 2.20 of the Investigator's Brochure.

Based on these considerations, the baroloop device has performance characteristics similar to the LivaNova VNS systems in terms of charge, pulse width and frequency used. The charge is biphasic and balanced asymmetrically so that the intensity of depolarizing stimulation is greater, but of shorter duration than the repolarizing phase which is of lower intensity and longer duration. In addition, the baroloop device is a multichannel stimulation device, and optimal electrode pairs may be selected to active the vagus with the lowest possible energy input. The baroloop cuff electrode has multiple, small active electrode areas, rendering the charge injection in any electrode pair closer to the Shannon Criteria, without reaching it. The pulse width can be as long as $500 \mu\text{s}$, and this enables the baroloop implant to reach and stimulate small axonal fibers. The physician may choose among a variety of presets, which are pre-defined sets of stimulation parameters (e.g., duty cycle, stimulus amplitude, and pulse

width) that may be selected through the Programmer to activate the baroreflex. The wave form of an individual stimulus for the baroloop system is shown below (Figure 1.).

Figure 1: Schematic of the elementary parameterization of a stimulation pulse

In Figure 1 above, the stimulation channel (not shown here) was set to apply a given number of pulses with a defined strength (current I), a given pulse width (PW) and repetition interval (1/F). Not shown either is the duty cycle based on intervals between bursts of pulses. To avoid polarization of the cathode, the pulses are biphasic and charge balanced ($Q_1=Q_2$).

In summary, the strength and magnitude of baroloop stimulation is comparable to existing VNS stimulation parameters. The conditioning of the stimulation is slightly better as the baroloop device applies charge balanced, biphasic pulses. The spatial pattern of selective stimulation made possible by the multielectrode baroloop cuff permits application of strong, local stimuli to activate specific, small circumferential sectors of the vagal nerve, where the relative number of baroreceptor active fibers may be increased. The temporal pattern of stimulation (in intermittent bursts) is unique as well, since the baroloop stimulation pattern may mimic the grouping of afferent sensory activity triggered by the blood pressure wave of the expelled blood that passes the aortic arch and carotid bifurcation.

2.5.4. The baroloop System: vagal nerve stimulation to control blood pressure

neuroloop has developed a novel cuff electrode for use with a safe and effective mechanism of vagal nerve stimulation to activate the baroreflex and lower blood pressure in the context of hypertension. The neuroloop device fits well within the current trends of treatment of hypertension in that resistant hypertension is remarkably common, and inadequate treatment of hypertension to achieve treated blood pressure levels less than 140/90 mm Hg (and better still according to current recommendations less than 130/80 mm Hg) is associated with increased risks of adverse cardiovascular outcomes from hypertension. Pharmacological therapy of hypertension is inadequate in many patients either because patients do not take the medicines, suffer side-effects from the medicines, or the medicines are ineffective controlling blood pressure. Given the novel design and treatment features of the neuroloop device, the Sponsor will conduct a First in Human Study to evaluate the safety and feasibility of treating hypertension using VNS.

2.5.5. VNS to Treat Hypertension

The vagal nerve consists of afferent and efferent fibers for visceral organs carrying information regarding autonomic functions. The vagus transmits afferent information about the internal state of the body to the central nervous system, and transmits efferent information from the central nervous system, especially autonomic control information from the brainstem to effector organs of the autonomic nervous system (largely the parasympathetic part of the autonomic nervous system) (Johnson and Wilson, 2018). Among many autonomic functions, which are under control of the vagal nerve, it is known that baroreceptive fibers merge with the vagal nerve (Benarroch, 2008). It is, however, not clear where they are located within the vagal nerve. In some mammals, the fibers are bundled in the aortic depressor nerve (ADN) (Kobayashi et al., 1999). Stimulation of ADN-fibers activates the baroreflex and therefore leads to a drop of blood pressure (De Paula et al., 1999; Fan and Andresen, 1998; Gao et al., 2006; Tosato et al., 2006). The cardiovascular efferents differs between the right and left vagal nerves; the right innervates the sinoatrial node, and the left innervates the atrioventricular node (Johnson and Wilson, 2018; Panebianco et al., 2016). Saxena et al. described the effect of acute vagal stimulation in humans, which resulted in blood pressure lowering that was dependent on the current- and frequency of stimulation (Ng et al., 2016). At higher currents, atrio-ventricular (AV) block and ventricular asystole were observed as side-effects during stimulation, which may result from direct activation of efferent cardiac fibers (Mirkovic et al., 2012). However, this was not a systematic evaluation of VNS and baroreflex activation as a therapy for hypertension, and the efficacy of chronic vagal nerve stimulation in humans to activate the baroreflex has not been proven. Therefore, neuroloop has developed a clinical feasibility study: A First-in-Human study will be performed to assess the efficacy/ feasibility and safety of blood pressure lowering in humans via stimulation of the left vagal nerve to activate the baroreflex.

2.6. Preclinical Experience with the baroloop System

The baroloop System has been subjected to a comprehensive pre-clinical testing program to verify design, safety, and performance against pre-specified engineering, mechanical and system requirements. Pre-clinical testing included bench, biocompatibility, animal, and sterilization testing. In addition to evaluation against internal specifications and international standards, the baroloop System was also tested in accordance with appropriate international standards as described in the Investigators Brochure for this First in Human Study.

Complete biocompatibility evaluation was performed on the baroloop device according to ISO10993, Biological Evaluation of Medical Devices Part 1: Evaluation and testing within a risk management process. After gathering physical and chemical data on the device, based on risk assessment, further studies were performed on baroloop device included physical and/or chemical information, cytotoxicity, sensitization, irritation, material related pyrogenicity, implantation studies (also included acute, subacute, sub-chronic and chronic studies), and genotoxicity. Based on overall biological evaluation performed on the device, baroloop device can be considered biocompatible without the need to perform pre-clinical additional tests and could be considered suitable for its clinical application study.

In conclusion, the baroloop System has been fully evaluated through pre-clinical testing per the identified risks and demonstrates compliance with its predetermined performance specifications.

Animal studies have been performed to further support the safety and performance of the baroloop System. The device elicited no adverse blood or tissue response, and no gross injuries were associated with the placement of the device, thereby demonstrating the safety

 neuroloop	Confidential	Protocol – The baroloop Study
--	---------------------	-------------------------------------

and feasibility of the device in an animal model (BL_ER_Efficacy_Report; BL_Safety_GLP_19-55_Interim_Report, BL_PCS2_Safety_GLP_19-55_Study_Report). Pre-clinical animal studies have been conducted and support the safety and performance of the baroloop System through simulated use under in vivo conditions in a porcine model (performance in minipig) and in an ovine model (safety in sheep).

3. Test System (Investigational Device)

3.1. Product name

baroloop®

3.2. General description

neuroloop has developed a platform based on thin-film technology for selective stimulation of the vagus nerve. The core part of the platform is a multi-channel electrode based on a thin-film cuff.

The goal of baroloop therapy is to achieve clinically effective blood pressure control while minimizing adverse reactions and provide superior usability of the implant for the surgeon, treating physician and the patients.

The system includes auxiliary devices and services to allow the patient to recharge the device and treating physicians to adjust the therapy.

The neuroloop product baroloop® is a stimulator platform for treating hypertension. The implantable parts of the stimulator platform will be used by the surgeon only. The non-implantable parts, as described in the following sections, interact with and direct the activity of the implanted system and will be used only by professionals in this study.

The implanted parts of the stimulator platform are intended to remain in the patient, whereas the programmer and recharging platform remain outside each patient's body. The recharging interval is every 1 to 4 weeks (depending on the stimulation parameters). However, patients enrolled in the study will have the device charged by professionals during protocol-required follow-up visits to the study site.

The nomenclature in the technical documentation for the implanted parts is as follows:

- The Lead consists of four elements: the “Cuff”, “Pill”, the “Cable” and the “Connector”.
 - The Cuff is a thin film electrode, which surrounds the nerve. The Cuff is wrapped around the left vagus nerve to establish an electrical connection to the nerve.
 - Please see the Instructions for Use, Section 2.11 of the Investigators Brochure and p. 8 of the Implantation Manual for information regarding available cuff sizes and selection criteria.
 - The Pill is the interface between Cuff and Cable, which is required to establish the electrical connection between thin-film and wires that communicate with the Implantable Pulse Generator (IPG).
 - The Cable consists of medical-grade, insulated wires encapsulated in a biocompatible mantle.
 - The Connector is the electrical interface between the Lead and the IPG.

 neuroloop	Confidential	Protocol – The baroloop Study
--	---------------------	-------------------------------------

- This stimulator device, the “Implantable Pulse Generator” (IPG) completes the stimulator platform. The IPG generates the stimulus as well as recording electrical signals derived from the Cuff electrodes and other components of the device. The IPG is controlled by an external programmer (see below).

The non-implanted parts are the following:

- A free-standing, wearable, transcutaneous charging device, the “Charger,” will be used to recharge the batteries within the IPG. The Charger is designed for professional use only . Besides the transfer of power, the Charger also transfers data from and to the IPG.
- A programming device, the “Programmer,” directs the IPG to provide vagal nerve stimulation tailored to the needs of each patient and accepts data from the IPG that was recorded to monitor the performance of the internal components of the baroloop. The Programmer is for professional use only.
- For the First-in-Human study, the Charger will be recharged using a laptop computer or USB power supply and a USB cable. The Charger will be used only in the professional environment (hospital or doctor’s office).

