4.24. Stimulation Settings/Titration First-in-Human

Blood pressure titration using VNS will take several 'titration sessions' to obtain optimal control of blood pressure. The titration sessions will take place weekly after the first titration is completed 14 days after surgery until the blood pressure has reached a target value less than the age-adjusted 2018 ESC/ESH treatment target office blood pressure (OBP). In between each titration session for the first four (4) weeks, the patient will return to the hospital or office where the titration takes place to have the IPG recharged, data downloaded from the IPG, and a check of OBP. Thus, there will be two alternating types of visits each week for the first 4 weeks of titration, one for titration, data downloading from the IPG and IPG charging and one for an OBP check, data downloading from the IPG and IPG charging.

After 4 weeks, titration may be done weekly, and the IPG charging may be done weekly when the titration is conducted. The titration process will continue until the target OBP is reached or the patient's responses to VNS are sufficiently reliable to allow less frequent follow-up after each new titration of OBP. Once a stable, target OBP is reached, blood pressure follow-up may occur at an interval appropriate for blood pressure control as determined by the treating physician.

During the first titration of baroloop stimulation, the Investigator should explore as fully as possible the range of responses to different electrode positions and stimulation settings so that an optimal set of stimulation settings may be selected with full knowledge of the range of responses in each subject at each visit.

During the titration of blood pressure responses to baroloop stimulation, each subject's blood pressure should be monitored continuously using a Finapres device. The patient should be supine and blood pressure and heart rate should be recorded continuously. After stable BP and HR are observed in the patient, the titration of the VNS may begin. Blood pressure responses to specific stimulation tests should be recorded by the Finapres device, and it is also important to record the baseline blood pressure and recovery periods after stimulation to characterize each patient's response to baroloop stimulation. The blood pressure should also

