If a 20% reduction in baseline blood pressure is greater than the age-adjusted OBP target, then the target blood pressure should be approached in a series of incremental steps in which an intermediate target blood pressure not below 80% of the baseline blood pressure is targeted. This intermediate target blood pressure should then be maintained for a week (at least) until the next visit for further titration, when a further 20% reduction in blood pressure may be targeted so long as the patient has no symptoms of dizziness, orthostatic hypotension or other adverse effects

Once an effective set of stimulation parameters has been selected, this setting should be used for treatment until the next study visit, when the blood pressure response can be re-evaluated, and stimulation parameters may be adjusted as appropriate to reach the goal of a blood pressure less than the age-adjusted OBP target.

Once the first treatment stimulation level has been selected, the patient should be observed in the hospital for 24 hours (as noted above). The titration of blood pressure will be retested after 24 hours prior to discharge following the titration strategy described above over a more limited range of electrode combinations and preset stimulation values. If the treatment is well tolerated and no adverse effects of VNS are identified during the hospital stay, the patient may be discharged on the prescribed pattern of VNS. Patients need not be hospitalized following subsequent blood pressure/stimulation titrations so long as the patient has no symptoms of dizziness, orthostatic hypotension or other adverse effects.

It is the Sponsor's expectation that most patients will achieve an OBP less than the age-adjusted target of hypertension treatment within a small number of weekly titration sessions. If the titration process persists beyond 12 sessions (~ 3 months), it is permissible to extend the interval between titrations up to six weeks. The patient and physician may work together to achieve a titration schedule that achieves the age-adjusted target OBP as quickly as is safe.

N.B.: The IPG should be charged at every visit to the physician's office for follow-up. In the first four weeks of titration, the IPG will be recharged twice a week. After four weeks of titration, the IPG may be charged weekly when the well-being of the patient will also be assessed. There is no home charging possible in this First in Human Study.

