4.31. Unscheduled Follow-up Visit

If an unscheduled follow-up visit is required, the study subject should be assessed for new or unresolved adverse events. Any testing required, including imaging studies, should be provided to the study Sponsor for DSMB adjudication. Office cuff blood pressure will be taken

and will be reviewed. Change of medications, diagnostic test results, or interventions should be documented.

4.32. 4.32 Schedule of Study Visits and Assessments

Table 3: Schedule of Study Visits and Assessments

Visit	Follow-up									Long Term Follow-up
	Visit 1	Visit 2	Visit Procedure	Discharge	14 Days (+/- 3 days)	Weekly Office visits (1x/2x)*	30 Days (+/- 7 days)	90 Days (+/- 14 days)	180 Days (+/- 14 days)	
Eligibility	✓	✓	✓							
Informed Consent	✓									
Medical History	✓									
Physical Examination	✓		✓		✓		✓	✓	✓	✓
Concomitant medications	✓	✓	✓		✓		✓	✓	✓	✓
Baseline 12 lead ECG	✓									
Blood Testing	✓			✓						
24 hour ABPM		✓					✓	✓	✓	✓
Medication compliance testing		✓					✓	✓	✓	✓
Quality of Life SF-36	✓	✓					✓	✓	✓	✓
neuroloop implantation			✓							
neuroloop titration*,**					✓	(✓)	✓	✓	✓	✓
IPG recharging and data downloading*					✓	✓				
Office cuff BP Measurement	✓	✓	✓	✓	✓	✓	✓	✓	✓	✓
Discharge				✓						
Adverse Events	✓	✓	✓	✓	✓	✓	✓	✓	✓	✓

*Titration after Day 14 takes place 1x per week. The second weekly visit through Day 30 is for Office BP and IPG battery charging only. After Day 30, only one visit per week for charging and (if necessary) titration is required.

**The heart rate and blood pressure will be recorded using a Finapres device during each titration.

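### The IPG charging provisions contradict one another, so stimulation through month 24 is not assured, and the SAP has no rule for blood pressure readings taken while stimulation has lapsed

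*Combined protocol and SAP*

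**What the plan says.** **Device need.** Section 3.2 states: "The recharging interval is every 1 to 4 weeks (depending on the stimulation parameters". It adds that "patients enrolled in the study will have the device charged by professionals during protocol-required follow-up visits to the study site". Section 4.24 closes the alternative: "There is no home charging possible in this First in Human Study".

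**Charging in section 4.24.** For the first four weeks of titration the IPG is charged twice a week. After that, one paragraph says "the IPG charging may be done weekly when the titration is conducted" and a later note says "After four weeks of titration, the IPG may be charged weekly when the well-being of the patient will also be assessed". The section lets visits become less frequent when responses are reliable. Once target pressure is stable, "blood pressure follow-up may occur at an interval appropriate for blood pressure control as determined by the treating physician". If titration runs past 12 sessions, "it is permissible to extend the interval between titrations up to six weeks". The same section also says to charge at every office follow-up visit.

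**Charging in section 4.32.** The Table 3 footnote keeps the second weekly visit through Day 30, then says: "After Day 30, only one visit per week for charging and (if necessary) titration is required". It gives no end date.

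**Visit lists.** Sections 4.26 to 4.30 (Day 30 to month 24) list titration, office pressure and 24-hour ABPM, but not charging. The synopsis follow-up schedule gives Day 14 and months 1, 3, 6, 12, 18 and 24, with no weekly visits.

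**Analysis.** Section 6.4 summarises ABPM and office pressure change at 1 to 24 months. Section 6.6 uses all available data without imputation. Neither mentions stimulation status.

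**The concern.** With professional charging only, the visit schedule is in effect part of the treatment: a subject who is not seen is not charged. If the permitted time between visits can exceed the device's recharging interval, stimulation may stop without anyone intending it.

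Two things are then at stake. First, subjects could have unplanned interruptions of stimulation. Second, the long-term blood pressure summaries would average readings taken on and off stimulation, with nothing in the data to separate them. A small mean change at month 12 could reflect either a weak effect or an uncharged device. Section 6.1 counts any blood pressure reduction resulting from the therapy towards a successful study, without naming the measure or the time point, so these summaries may bear on that judgement. With at most 10 subjects, one reading carries at least 1/10 = 10% of the weight of a visit mean.

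**Working it through.** The plan states no figure to reproduce. The check sets the passages side by side and compares intervals.

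**Inputs**
- Recharging interval: 7 to 28 days (section 3.2).
- First titration: Day 14, or by Day 21 if the subject is not ready (section 4.23).
- Twice-weekly charging: first four weeks of titration (4.24); through Day 30 (Table 3 footnote).
- Charging afterwards: weekly, optional wording (4.24); weekly, required (footnote).
- Maximum follow-up interval once target is stable: none given (4.24).
- Visit windows: Day 30 ± 7; Day 90 and later ± 14 (sections 4.26 to 4.30).

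**1. End of twice-weekly charging.** Under 4.24: 14 + 28 = Day 42, or 21 + 28 = Day 49. Under the footnote: Day 30. The passages differ by 12 to 19 days.

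**2. Can the named visits alone meet the recharging interval?** The shortest possible gap after Day 30 is from a late Day 30 visit to an early Day 90 visit: (90 − 14) − (30 + 7) = 76 − 37 = 39 days. This exceeds 28. The next gap, Day 90 to Day 180, is at least (180 − 14) − (90 + 14) = 62 days, and the later ones are longer. The named visits cannot meet the interval by themselves. Everything depends on the additional visits, and those are what the passages disagree about.

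**3. If the footnote governs.** Nominal spacing is 7 days, within the 1-to-4-week interval, so no gap arises. The implied number of visits from Day 30 to Day 730 is (730 − 30)/7 = 100. The synopsis shows none of them.

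**4. If a site follows 4.24.** Weekly charging is worded as *may*, is linked to titration in one place, and follow-up has no upper limit once target is stable. Nothing in that section keeps the time between charges within 28 days.

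**5. Illustration only.** Assume that one charge lasts the stated 1 to 4 weeks, and that a site charges only when it titrates, at six-week spacing. Coverage is then 1/6 = 17% to 4/6 = 67% of the interval. The documents give neither run time to depletion nor any reserve, so this is not an estimate.

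**6. Stimulation record.** Section 3.12 says the IPG records impedance, electrode continuity and heart rate. It mentions no log of stimulation or battery state, so stimulation status cannot be assumed to be recoverable from the downloaded data.

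**The case against.** The strongest reply is that Table 3 settles the matter. Its footnote requires a weekly charging visit and makes titration at that visit conditional, so a long titration interval is compatible with weekly charging. The weekly visits have their own column in Table 3, and they can be the protocol-required visits that section 3.2 has in mind. On this view, *may* in 4.24 is only a step down from twice weekly.

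Much of this stands. A reader might infer that 4.24 allows six-week charging intervals. It does not say so: the six weeks apply to titrations, and the physician-chosen interval applies to blood pressure follow-up. A reader might also infer that subjects will be off stimulation when long-term pressure is measured. That is not shown either. The documents do not say what happens beyond the recharging interval, and 4.24 calls for charging at every visit, so an ABPM begun after charging would run on a charged device; the order is not stated. Nor does any passage prescribe charging only at the 3- to 6-monthly visits, so low coverage figures built on those gaps would be unsupported. The tick positions in Table 3 come from an extracted table and should be checked in the original.

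The reply does not remove the conflict. Required in one place and optional in another is not aligned wording, the footnote has no end date, and the Day 30 against Day 42 to 49 difference is not explained by any reading of *may*. It is also fair to say that the blood pressure endpoints are secondary and descriptive, and that the primary endpoints are MAE at six months and technical success at Day 14/21.

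**Conclusion.** The charging provisions in sections 3.2, 4.24 and 4.32 do not agree, and the later visit lists and the synopsis do not resolve them. That follows from the text alone. A lapse in stimulation is a possibility, not a demonstrated event: there is none if the weekly footnote is followed, and its extent is unknown under 4.24 because battery reserve is not stated. The 17 to 67% illustration rests wholly on the assumption that one charge lasts the stated interval and that charging follows a six-week titration interval.

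Whichever passage governs, the plan has no rule for identifying or reporting blood pressure readings taken while stimulation was interrupted. The consequence is confined to the secondary blood pressure summaries, any use of them in the success statement of section 6.1, and subjects' continuity of treatment. It deserves correction because it is cheap to fix now and may not be recoverable after data collection.

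**What to change.** **Protocol.** Reconcile the synopsis schedule, section 3.2, section 4.24, the visit lists in 4.25 to 4.30, and Table 3 with its footnote, so that the permitted visit interval and the recharging interval agree through month 24 and twice-weekly charging has one stated end. The sponsor must decide which passage governs. Check the Table 3 charging row against the original layout.

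**SAP.** For each ABPM and office reading, record whether stimulation was active. Derive this from IPG data if the device logs it; otherwise add a CRF field at each visit. Report blood pressure change overall and for readings with confirmed active stimulation, with the number of readings in each summary.

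**Cost.** Wording changes and one derived flag or CRF field. If weekly charging is confirmed, the burden of about 100 visits per subject after Day 30 has to be stated openly.
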